Participants who receive any of the prohibited treatments or undergo surgery during the Screening Period will not start the intervention period. They may, however, be rescreened following the procedures described in the SoA ([Section 1.3](#)).

Participants who use INCS between Visit 2 and Week 24 for whatever reason will discontinue the IMP administration.

Permitted concomitant medication

The following treatments are allowed throughout the study unless otherwise specified:

- Intranasal corticosteroids to treat other coexisting diseases (such as allergic rhinitis) are allowed after Week 24 as needed.
- Nasal normal saline.
- Single topical decongestant administration such as oxymetazoline hydrochloride (to reduce swelling and widen the path for the endoscope) and topical anesthetics such as lidocaine are allowed before endoscopy.
- Short-acting $\beta 2$ -adrenergic receptor agonists, long-acting $\beta 2$ -adrenergic receptor agonists, and long-acting muscarinic acetylcholine receptor antagonists.
- Methylxanthines (eg, theophylline, aminophyllines).
- Inhaled corticosteroids.
- Systemic antihistamines.

- Leukotriene antagonists/modifiers are permitted during the study, only for participants who were on a continuous treatment for ≥ 30 days before Visit 1.
- Allergen immunotherapy in place for ≥ 3 months before Visit 1 is permitted.
- Paracetamol/Acetaminophen, at doses of ≤ 2 g/day, is permitted for use any time during the study.

Other concomitant medication may be considered on a case-by-case basis by the Investigator in consultation with the Medical Monitor if required.

Rescue medication including antibiotics, short courses of SCS for treatment of CRSwNP as described in [Section 6.8.1](#), or short courses of SCS to treat other serious coexisting diseases (such as asthma exacerbation) or for AEs is allowed.

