6.8.1 Rescue medicine and procedures

During the study intervention period, based on clinical evaluation, in case of worsening of signs and/or symptoms requiring medical intervention, the following rescue medications/procedures may be employed as per Investigator's judgment:

1. Systemic (eg, oral) corticosteroids up to 2 weeks
2. Antibiotics for the treatment of acute sinusitis less than 2 weeks after Visit 2
3. Sinonasal surgery

Participants receiving rescue treatment other than surgery during the study should continue on IMP unless the Investigator decides to withdraw the study intervention. Before starting treatment with SCS, participants should come to the study site for the clinical assessments including endoscopy.

For participants who undergo or plan to have surgery for NP, the Investigator may decide to continue IMP up to the time of surgery or EOT, whichever date comes first. At the time of surgery, participants will be permanently discontinued from study intervention and assessed as soon as possible using the procedures normally planned for the EOT/EOS Visit as described in the SoA ([Section 1.3](#)).

If the surgery is to be performed during the intervention period, an AE or SAE page will be completed. If surgery is scheduled after the planned EOS, the EOT/EOS Visit will not be delayed. The surgery will be followed up by the Investigator or the participant's physician with general medical practice.

In any case, participants who prematurely discontinue the treatment will be encouraged to return to the study site for the efficacy and safety assessments planned at the EOT/EOS Visit (refer to SoA [[Section 1.3](#)]).

The date and time of rescue medication administration as well as the name and dosage regimen of the rescue medication must be recorded. For participants who undergo sinonasal surgery for NP, the reason (worsening signs and/or symptoms during the study), the expected and real surgery

dates, and the type and outcome of surgery will be recorded. For participants who plan to have sinonasal surgery for NP, the reason (worsening signs and/or symptoms during the study), the expected and real surgery dates, and the type of surgery will also be recorded in the e-CRF.

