Key secondary endpoints	Change from baseline to Week 24: 
 
• Bilateral NPS
 
• NC symptom severity score
 
• LMK score
 
	PP	The intercurrent events will be handled as follows: 
 
• Taking rescue medications or undergo surgery prior to Week 24: data will be set to missing after the medication usage, and the participant's worst postbaseline value on or before the time of the medication usage or surgery will be used to impute the missing Week 24 value (for participants whose postbaseline values are all missing, the baseline will be used to impute) (hypothetical strategy)
 
• Discontinuing the treatment prematurely (Participants who did not take rescue medications or undergo surgery): all data collected after treatment discontinuation will be used in the analysis (treatment policy strategy).
 
	All imputed, complete data will be analyzed by descriptive statistics and 95% CI. The summarized mean changes obtained from each imputed dataset will be combined using Rubin's rule for a single estimate.

Estimands				
Endpoint Category	Endpoint	Population	Intercurrent event(s) handling strategy (The missing data handling)	Population-level summary (Analysis method)
Other secondary efficacy endpoints	
 
• Change from baseline to Week 24:
 
• Total symptom score
 
• Loss of smell symptom severity score
 
 Visual analogue scale for rhinosinusitis		In addition, the missing data imputation rules are as follows: 
 
• After treatment discontinuation due to lack of efficacy prior to Week 24: WOCF approach will be used to impute the missing Week 24 value if needed
 
• After treatment discontinuation due to reasons other than lack of efficacy prior to Week 24: multiple imputation approach assuming missing at random will be used to impute the missing Week 24 value, and this multiple imputation will use all participants, excluding participants who have taken rescue medications or undergone surgery on or before Week 24 and excluding participants who discontinue due to lack of efficacy on or before Week 24.
 
	

Estimands				
Endpoint Category	Endpoint	Population	Intercurrent event(s) handling strategy (The missing data handling)	Population-level summary (Analysis method)

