## ***Rescue***

Participants who have undergone surgery or received SCS for any reasons are considered rescued. NP surgery and SCS use will be determined by the corresponding eCRF pages.

The date of rescue will be the earliest date of having undergone surgery or received SCS for any reason.

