#### **4.4.1.2 Main analytical approach**

##### Handling of missing data

Each of the 3 key secondary efficacy endpoints will be analyzed using the PP population and a hybrid method of worst observation carried forward (WOCF) and multiple imputation. For participants taking rescue medications or who undergo surgery, their data after the medication usage or surgery will be set to missing, and the worst postbaseline value on or before the time of the medication usage or surgery will be used to impute the missing Week 24 value. Participants who discontinue the treatment prematurely are encouraged to follow the planned clinical visits, and in those participants who did not take rescue medications or undergo surgery, all data collected after treatment discontinuation will be used in the analysis. For these participants, missing data may still happen despite all efforts to collect the data after treatment discontinuation. For participants who discontinue due to lack of efficacy, all data collected after discontinuation will be used in the analysis, and a WOCF approach will be used to impute the missing Week 24 value if needed. For participants who discontinue not due to lack of efficacy, a multiple imputation approach assuming missing at random will be used to impute the missing Week 24 value, and this multiple imputation will use all participants, excluding participants who have taken rescue medications or undergone surgery on or before Week 24 and excluding participants who discontinue due to lack of efficacy on or before Week 24. All of the imputed complete data will be analyzed by descriptive statistics with the 95% CI. The summarized mean changes obtained from each imputed dataset will be combined using Rubin's rule for a single estimate.

The following steps will be used to create the primary imputed datasets:

- Impute any missing baseline values with the mean baseline value of all participants with non-missing baseline data.
- For participants who are rescued (undergo surgery for NP or receive SCS for any reason) or discontinue treatment early due to lack of efficacy:
  - Set all data on or after earliest date of rescue or treatment discontinuation to missing.
  - Replace all missing values with the worst observation prior to the missing data through Week 24, including baseline values.
- For participants who are not rescued, discontinue treatment for reasons other than lack of efficacy, or complete the study:

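### SAP 4.4.1.2 gives two incompatible rules for Week 24 values after a lack-of-efficacy stop or rescue, and its imputation steps do not follow its own narrative

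*SAP*

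**What the plan says.** **Lack-of-efficacy stops.** The narrative of SAP 4.4.1.2 says: "For participants who discontinue due to lack of efficacy, all data collected after discontinuation will be used in the analysis". Worst-observation carried forward (WOCF) then applies only where Week 24 is missing. Protocol 9.3.3 has the same rule. SAP Table 3 keeps post-stop data for any unrescued discontinuation and likewise limits WOCF after a lack-of-efficacy stop to a missing Week 24.

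**Rescue.** The narrative says that the "worst postbaseline value on or before the time of the medication usage or surgery will be used to impute the missing Week 24 value". Table 3 and protocol 9.3.3 agree and give baseline a fallback role only: "for participants whose postbaseline values are all missing, the baseline will be used to impute". The narrative itself omits that fallback.

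**The steps.** The list that closes SAP 4.4.1.2 treats rescued participants and lack-of-efficacy stops as one group, with two instructions: "Set all data on or after earliest date of rescue or treatment discontinuation to missing" and "Replace all missing values with the worst observation prior to the missing data through Week 24, including baseline values". It then combines this group with the remaining participants and runs 40 regression imputations. The narrative fits the imputation without rescued participants and lack-of-efficacy stops.

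**Reach.** SAP 4.4.2.2 analyses total symptom score (TSS), loss of smell and the rhinosinusitis VAS by similar methodology. SAP 4.1 defines rescue broadly: "Participants who have undergone surgery or received SCS for any reasons are considered rescued".

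**Change log.** SAP Appendix 2 lists two changes from the protocol: the treatment-emergent period and the definition of rescue. The SAP version history denies any major departure from the protocol's statistical features.

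**The concern.** A programmer working from the steps and one working from the narrative would produce different Week 24 datasets for the same participants. Protocol 3.1 says that NPS, nasal congestion (NC) and Lund Mackay (LMK) change are there to show efficacy similar to EFC14280, so the main estimate of each should not depend on which half of a section is programmed. In an open-label study of about 25 participants, an unresolved rule also leaves the choice to be made when outcomes can already be known.

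The events can occur. Protocol 7.1 and 7.1.1 ask that participants who stop treatment stay in the study and be followed to the scheduled end, so a Week 24 score after a lack-of-efficacy stop is expected. Protocol 6.8 provides that "short courses of SCS to treat other serious coexisting diseases (such as asthma exacerbation) or for AEs is allowed", so a participant whose polyps are shrinking can become a rescue case. Protocol 6.8.1 adds: "Before starting treatment with SCS, participants should come to the study site for the clinical assessments including endoscopy". If systemic corticosteroids (SCS) start that same day, the text keeps the endoscopy value and the steps delete it.

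**Working it through.** **Side by side**

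| Situation | Narrative, Table 3, protocol 9.3.3 | Steps |
|---|---|---|
| Lack-of-efficacy stop, Week 24 observed | Observed value used | Deleted; worst earlier value used |
| Rescue, value on the rescue date | Kept as a candidate | Deleted |
| Rescue, role of baseline | Fallback only (Table 3, protocol) | Candidate or fallback, depending on reading |
| Imputation model | Fitted without these participants (narrative, Table 3 and protocol) | Regressions run after both datasets are combined |

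Rows 1, 2 and 4 conflict on any reading. Row 3 conflicts only if the closing words on baseline make it a candidate. On that reading the imputed value is the maximum of baseline and earlier values, so the change is never below 0 and nobody in either group can show improvement.

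**Inputs.** The plan gives no figure for this rule. The number of participants comes from protocol 9.1: 20/(1 - 0.20) = 25. The stated 90% also reproduces, since P(X ≥ 10 | n = 20, p = 0.62) = 0.908, but nothing here depends on it.

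**Formula.** Let d be the change under the steps minus the change under the text. For k participants, the mean shifts by k × d/N: 0.04d each at N = 25, 0.05d each at N = 20.

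**Hypothetical cases (baseline NPS 6, N = 25)**

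1. Lack-of-efficacy stop, worst earlier value 6, observed Week 24 of 4. Text 4 - 6 = -2; steps 6 - 6 = 0; shift 2/25 = +0.08. This holds on either reading of the baseline clause.
2. The same, but observed Week 24 of 7. Text +1; steps 0; shift -1/25 = -0.04.
3. SCS for asthma after visits of 5, 4, 3. Text 5 - 6 = -1. Steps with baseline as candidate: 0, shift +0.04. Steps with baseline as fallback: -1, shift 0.
4. Visits of 5, 5, 5 and a pre-SCS endoscopy of 7 on the rescue date. Text +1. Steps with baseline as candidate: 0, shift -0.04. Steps with baseline as fallback: 5 - 6 = -1, shift -2/25 = -0.08.

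Case 4 also assumes that an unscheduled endoscopy counts as a WOCF candidate, which the SAP does not say.

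**LMK.** No CT is scheduled between screening and Week 24, so after rescue both rules usually return baseline. After a lack-of-efficacy stop the rules differ only if a Week 24 CT was taken, and protocol 7.1.1 leaves CT out of the discontinuation assessment. If one was taken, an assumed fall from 18 to 13 gives text -5, steps 0, shift 5/25 = +0.20.

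**Simulation.** Assumed inputs: n = 25, mean NPS change -1.8, SD 1.7, event after Week 16, Week 24 observed, nothing else missing. Mean shifts over the scenarios tried:

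- One lack-of-efficacy stop: -0.013 to 0.062. Three: -0.042 to 0.196.
- One rescue: -0.034 to 0.034. Three: -0.125 to 0.100. The upper ends take baseline as a candidate.

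These are scenario averages, not limits: case 1 (+0.08) lies outside the one-stop range, and three such cases give 3 × 2/25 = 0.24. For scale, the assumed 95% CI half-width is 2.064 × 1.7/5 = 0.70. NC, TSS, smell, VAS and the effect of the imputation order were not sized.

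**The case against.** **The baseline clause may be shorthand.** It can be read as the fallback that Table 3 and the protocol spell out. That stands, so any result resting on baseline as a candidate is conditional. It does not remove the deletion of data after a lack-of-efficacy stop or of rescue-date values.

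**The same-day endoscopy is uncertain.** The protocol asks for it before SCS, not on the same day. SAP Table 10 and section 5.4.5 keep only the assessment nearest the target day in each window. A day-130 endoscopy would lose to a day-113 visit, and a day-150 one falls in the Week 24 window (141 to 224). That stands too, and is a reason to state the rule.

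**The consequence is limited.** No hypothesis is tested, the key secondaries have no similarity margin, and the primary responder analysis has its own nonresponder rule. The mITT analysis in SAP 4.4.1.3 restates the text rule, and the by-visit summaries in 4.5.2.3 use no imputation. This limits the weight of the point. It does not say which main estimate will be reported.

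**Stronger readings to resist.** A reader might infer that the steps always understate benefit. Cases 2 and 4 go the other way, and the documents give no event mix from which to call either direction usual, least of all for rescue. A reader might also infer that Appendix 2 hides a change. The documents do not show which rule was intended: if the steps are a drafting slip, there is no change to log.

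**Conclusion.** The contradiction is real and should be fixed. SAP 4.4.1.2 cannot be programmed as written, because its steps and its narrative disagree on three matters: data after a lack-of-efficacy stop, values on the rescue date, and who enters the imputation model. Baseline as a worst-value candidate is a fourth, conditional on reading. If the steps are intended, they depart from protocol 9.3.3 without an entry in Appendix 2.

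The size is 0.04d per affected participant at N = 25, in either direction. It is modest beside an assumed half-width of 0.70, and zero if no such event occurs. The number of events is not in the documents, and the simulated figures rest on assumed inputs. LMK is exposed mainly through lack-of-efficacy stops, and only where a Week 24 CT was done. The primary endpoint is unaffected.

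**What to change.** Before efficacy review, reconcile the steps, the narrative and Table 3 to one rule. To match protocol 9.3.3:

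1. After a lack-of-efficacy stop, keep observed data and use WOCF only if Week 24 is missing. State whether baseline counts in that WOCF.
2. After rescue, remove only data later than the rescue date. Use the worst value after baseline up to and including that date, with baseline only where there is none.
3. Fit the multiple imputation without these participants and append their records afterwards.
4. State whether an unscheduled endoscopy before SCS is a WOCF candidate, given the Table 10 windows.

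If the steps are the intended rule, log the departure in Appendix 2 and revise Table 3 and the narrative to agree. Either way, state that the same handling applies to the mITT analysis in SAP 4.4.1.3.

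The cost is SAP wording and programming. SAP 4.1 already defines the rescue date, and no new data are needed.

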9.3.3 Key secondary efficacy endpoints

- Change from baseline to Week 24 in bilateral NPS
- Change from baseline to Week 24 in NC symptom severity score using the CRSwNP nasal symptom diary (refer to [Section 8.1.2](#) for the details of NC symptom severity score assessment)
- Change from baseline to Week 24 in opacification of sinuses assessed by CT scan using the LMK score (refer to [Section 8.1.3](#) for the details of LMK score)

Handling of missing data

Each of the 3 key secondary efficacy endpoints will be analyzed using a hybrid method of worst-observation carried forward (WOCF) and multiple imputation. For participants taking selected prohibited medications and/or rescue medications or who undergo surgery (details of selection will be specified in the SAP, refer to [Section 6.8.1](#)), their data after the medication usage or surgery will be set to missing, and the worst postbaseline value on or before the time of the medication usage or surgery will be used to impute the missing Week 24 value (for participants whose postbaseline values are all missing, the baseline will be used to impute). Participants who discontinue the treatment prematurely are encouraged to follow the planned clinical visits, and in those participants who did not take the selected prohibited medications and/or rescue medications or undergo surgery, all data collected after treatment discontinuation will be used in the analysis. For these participants, missing data may still happen despite all efforts to collect the data after treatment discontinuation. For participants who discontinue due to lack of efficacy, all data collected after discontinuation will be used in the analysis, and a WOCF approach will be used to impute the missing Week 24 value if needed. For participants who discontinue not due to lack of efficacy, a multiple imputation approach assuming missing at random will be used to impute the missing Week 24 value, and this multiple imputation will use all participants, excluding participants who have taken the selected prohibited medications and/or rescue medications or undergone surgery on or before Week 24 and excluding participants who discontinue due to lack of efficacy on or before Week 24. All of the imputed complete data will be analyzed by descriptive statistics with the 95% CI. The summarized mean changes obtained from each imputed dataset will be combined using Rubin's rule for a single estimate.

Other secondary efficacy endpoints

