## VERSION HISTORY

This statistical analysis plan (SAP) for study LPS16872 is based on the protocol version 1 dated 11-May-2021. There are no major changes to the statistical analysis features in this SAP compared to those in the protocol.

This SAP will be finalized before efficacy review.

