- Create 1 dataset with monotone missing pattern using the Markov Chain Monte Carlo (MCMC) method including values at all applicable visits through Week 24 in chronological order including baseline.
- For participants having missing data at Week 24 regardless of reason(s), a multiple imputation (MI) approach will be used to impute the missing endpoint value
- Set both datasets together.
- The remaining missing data will be imputed 40 times using the regression method for the monotone pattern with adjustment for values at all applicable visits through Week 24 in chronological order including baseline.
- Applying Rubin's rule to combine analysis results (means and standard errors) from 40 imputations using PROC MIANALYZE for the final estimated mean and 95% CL.

Missing data related to the key secondary endpoints will be tabulated including by relation to the COVID-19 pandemic. If necessary, additional supplementary analyses will be presented.

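### SAP 4.4.1.2 keeps rescued and lack-of-efficacy participants out of the imputation model in its narrative, but its step list merges their filled rows in before the regression

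*SAP*

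**What the plan says.** The rule on who feeds the model is stated consistently. The SAP 4.4.1.2 narrative has "this multiple imputation will use all participants, excluding participants who have taken rescue medications or undergone surgery on or before Week 24", and adds a second group: "excluding participants who discontinue due to lack of efficacy on or before Week 24". SAP Table 3 repeats both exclusions in the per-protocol and mITT rows. Protocol 9.3.3 has the same rule ("and excluding participants who discontinue due to lack of efficacy on or before Week 24"). It also names selected prohibited medications, which the SAP drops and declares as a change.

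The step list later in 4.4.1.2 runs in this order:

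1. For rescued and lack-of-efficacy participants: "Replace all missing values with the worst observation prior to the missing data through Week 24, including baseline values".
2. For the others: "Create 1 dataset with monotone missing pattern using the Markov Chain Monte Carlo (MCMC) method".
3. "Set both datasets together".
4. "The remaining missing data will be imputed 40 times using the regression method for the monotone pattern", adjusting for the earlier visits and baseline.
5. Pool the 40 results by Rubin's rule.

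On departures from the protocol, the SAP version history says "There are no major changes to the statistical analysis features in this SAP compared to those in the protocol". SAP section 5.2 lists two changes, to the treatment-emergent period and to the rescue definition. Neither concerns the imputation donors.

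**The concern.** The steps create only two datasets, so the natural reading of the merge is that the filled failures join everyone else before the regression that generates the missing Week 24 values. The exclusion is then respected at the MCMC stage and lost at the regression stage. Failures would count once through their own filled value and again through the values drawn for participants who left for unrelated reasons.

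LMK is the most exposed endpoint. CT is done at screening, Week 24 and Week 52, so through Week 24 baseline is the only predictor. A participant rescued before the Week 24 scan has only baseline to carry, so that row enters with a change of exactly zero. Missing LMK values are plausible, because protocol 7.1.1 omits the CT from the assessments made after permanent discontinuation.

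At stake are the means and confidence intervals of the three key secondary endpoints. Protocol sections 3.1 and 4.2.2 intend these to show efficacy similar to EFC14280. Two careful programmers could report different values from the same SAP.

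**Working it through.** **Inputs from the documents.** N = 25, allowing for 20% drop-out (protocol 9.1, SAP 2). That figure reproduces: P(X ≥ 10 | n = 20, p = 0.62) = 0.908 against the stated 90%, and 20/0.8 = 25. Planned drop-out is therefore 5 of 25. The documents give no mean change or SD for LMK or NPS, so everything below rests on assumptions.

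**LMK by hand.** Assume a mean change of −6 in completers, zero change in the *w* filled rows, similar baselines in both groups, and *m* participants needing imputation.

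- Mean imputed change, filled rows excluded: −6.
- Mean imputed change, filled rows as donors: −6 × (25 − m − w)/(25 − m).
- Shift in the overall mean: (m/25) × 6 × w/(25 − m).

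| w filled | m missing | affected | imputed change, merged | shift in overall mean |
|---|---|---|---|---|
| 2 | 3 | 5 (20%) | −6 × 20/22 = −5.45 | 3/25 × 6 × 2/22 = 0.065 |
| 3 | 2 | 5 (20%) | −6 × 20/23 = −5.22 | 2/25 × 6 × 3/23 = 0.063 |
| 4 | 3 | 7 (28%) | −6 × 18/22 = −4.91 | 3/25 × 6 × 4/22 = 0.131 |
| 4 | 5 | 9 (36%) | −6 × 16/20 = −4.80 | 5/25 × 6 × 4/20 = 0.240 |

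The other splits of five give less: 0.046 for 1 filled and 4 missing, 0.040 for 4 and 1. With w = 0 or m = 0 the shift is exactly zero. A simulation of the last two rows (150 trials each, 40 imputations) gives 0.126 and 0.240, in line with the formula.

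For scale, if the SD of LMK change is 4 to 5, the standard error is 4/√25 = 0.8 to 5/√25 = 1.0. Shifts of 0.063 to 0.240 are then between 0.063/1.0 = 6% and 0.240/0.8 = 30% of one standard error.

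**NPS by simulation.** Intermediate visits also act as predictors here, so no simple formula applies. Assumed: n = 25; baseline and Weeks 4, 8, 16 and 24; mean Week 24 change −1.5 or −2.5; SD rising from 1.0 to 1.7; sequential Bayesian regression; 40 imputations; Rubin's rule; 400 replicates per case. Imputed changes and standard errors are medians over replicates, and shifts are means.

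| mean change | filled / missing | imputed change, merged vs excluded | shift in overall mean | SE, merged vs excluded |
|---|---|---|---|---|
| −1.5 | 1 / 1 | −1.45 vs −1.50 | 0.001 | 0.355 vs 0.355 |
| −1.5 | 3 / 3 | −1.36 vs −1.59 | 0.026 | 0.380 vs 0.383 |
| −1.5 | 5 / 5 | −1.12 vs −1.52 | 0.074 | 0.401 vs 0.423 |
| −2.5 | 3 / 3 | −2.18 vs −2.50 | 0.036 | 0.408 vs 0.402 |
| −2.5 | 5 / 5 | −1.92 vs −2.56 | 0.113 | 0.448 vs 0.451 |

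Over all cases run (1 to 5 filled, 1 to 5 missing) the overall mean moves by 0.001 to 0.113 points, always toward less improvement, against a standard error of about 0.35 to 0.45.

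**The case against.** A reader might infer that the SAP positively instructs the failures to be used as donors, so that no program could satisfy both texts. The documents do not go that far. No step names the rows that fit the regression, and the two datasets being combined are never defined. The step just before the merge already calls for multiple imputation of missing Week 24 values, so the list mentions imputation on both sides of the merge. The indentation in the available text does not show reliably which steps belong under the non-rescued group. A program could stack all records, flag the filled ones and fit the regression without them, which would respect both the step order and the exclusion.

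That stands, but it does not remove the problem. The flag is nowhere in the steps, and a programmer who follows them as written would not add it.

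The other objections concern size, and they stand too. The larger LMK shifts need 28% to 36% of participants affected, against a planned drop-out of 20%. That 20% is not a strict cap, since rescued participants may stay on treatment. No hypothesis is tested, and the shift cannot make the results look more like EFC14280 by inflating improvement. For the three supportive endpoints the SAP says only that the methodology is similar, although protocol 9.3.3 applies the same hybrid approach to them.

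**Conclusion.** The text contradicts itself on who feeds the imputation model. The narrative, both Table 3 rows and the protocol agree with each other; the step list, read literally, is the outlier, and the departure is not recorded.

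The consequence is limited to the Week 24 continuous secondary endpoints: three key, and three supportive by reference. The direction is conservative, and the effect vanishes if nobody is filled or nobody needs imputation. Otherwise it is small beside the standard error, on the assumed means, SDs and counts above.

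A reader might conclude that the secondary results would be seriously biased, or that the main finding is at risk. Neither follows. The primary responder endpoint uses nonresponder imputation and never enters these steps. Severity is low to moderate: a wording conflict with a modest numerical effect, worth settling before efficacy data are reviewed.

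**What to change.** Reorder the steps in SAP 4.4.1.2. Run both the MCMC step and the 40 regression imputations only on participants who were neither rescued nor discontinued for lack of efficacy. Append the worst-value-filled records, unchanged, to each of the 40 completed datasets. Then compute the means and apply Rubin's rule. Name the datasets so that the merge is unambiguous.

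If the merged model is in fact intended, correct the narrative and Table 3 instead, and record the departure from protocol 9.3.3 in SAP section 5.2 with its reason.

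The reordering costs about two lines of SAP text and a change in program order. It needs no extra data and does not change the sample size.
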